8.4.5 Serum Tryptase Assessment		
Initial text: The actual collection time must be recorded entered into the subject's	Modified: The actual collection time must be recordedentered into the subject's	
record/source documents and transcribed to the CRFaccordingly.	record/source documents and transcribed to the CRFaccordingly.	
Rationale: To provide clarity for appropriate documentation.		
8.4.8 Pharmacokinetic Assessments		
Initial text:	Modified:	
• Additional samples will be collected on the following day 24 hours (±1 hour) post prior injection of VP-315.	• Additional samples will be collected on the following day 24 hours (±1 hour) post prior Day 1 first injection of VP-315 (prior to Day 2 injection).	
Rationale: To provide clarification for timing of PK samples.		
8.5.1 Lesion Evaluation		
Initial text:	Modified:	
All specimens (including HISTORICAL samples) will be sent as slides to the central dermatopathologist for confirmation of eligibility.	All specimens (including HISTORICAL samples) will be formalin-fixed and paraffin embedded (FFPE) and H&E stained slides of specimen slices will be	
In accordance with the procedures noted in Table 8-1, all target and nontarget BCC lesions will be surgically excised with a 3 mm- margin 4 to 6 weeks (Part 1) and 12 to 13 weeks (Part 2) after receipt of the W1D1 injection; slides will be sent to the central dermatopathologist for analysis/histology. If a lesion has clinically cleared, the area where the lesion was will be excised accordingly.	prepared and reviewed locally to determine sent as slides to the central dermatopathologist for confirmation of eligibility. The H&E stained slides will be sent to the central lab for imaging and high quality images of the slides will be sent to the central dermatopathologist for confirmation of analysis/histology.	

Initial Text	Added, Deleted, or Modified Text		
	In accordance with the procedures noted in Table 8-1, all target and nontarget BCC lesions will be surgically excised with a 3 mm- margin 4 to 6 weeks (Part 1) and 12 to 1314 weeks (Part 2) after receipt of the W1D1 injection and tissue specimens preserved by FFPE. If a lesion has clinically cleared, the area where the lesion was will be excised accordingly. Both the screening and post-excision tissue blocks will be sent to the central lab for analysis of immune activation biomarkers including TILs by multiplexed IF-IHC, as well as for sequencing of genomic DNA from the lesion specimens to assess changes in T-cell receptor clonality.; slides will be sent to the central dermatopathologist for analysis/histology. If a lesion has clinically cleared, the area where the lesion was will be excised accordingly.		
Rationale: To provide updated central lab information on the process for BCC tissue samples and analysis.			
8.8 Assessment of the Immunological Response to VP-315 Treatment			
Initial text:	Modified:		
In a subset of subjects, the anti-tumor immunological response to VP-315 treatment will be assessed in the excised tissue obtained from basal cell tumor biopsies performed at pre-screening (baseline) and at the approximate 12-week post-treatment visit, as well as in peripheral blood samples acquired at the same time points.			
Rationale: To include the window of the post-treatment visit.			
10.2 Dose-limiting Toxicity/Treatment-related Adverse Event of Spec	ial Interest		
Initial text:	Modified:		
In Part 1, any subject who experiences a DLT/TRAE SI will receive no further VP-315.	In Part 1, any Any subject who experiences a DLT/TRAE SI will receive no further VP-315.		
If the DLT is caused by an unexpected drug-related event that is not listed in the consent form, Sponsor will revise the consent form appropriately and submit it to the IRB.	If the DLT/TRAE SI is caused by an unexpected drug-related event that is not listed in the consent form, Sponsor will revise the consent form appropriately and submit it to the IRB.		
Rationale: To provide clarification with TRAE SI.			

## 1. PROTOCOL SYNOPSIS

**Protocol Title:** A Phase 2, Multicenter, Open-label, Proof-of-Concept Study with Safety Run-in to Evaluate the Safety, Pharmacokinetics, and Efficacy of VP-315 in Adult Subjects with Basal Cell Carcinoma

Phase: 2

**Indication:** basal cell carcinoma (BCC)

# Hypotheses, Objectives, and Endpoints:

There is no formal hypothesis testing in this study. The following objectives and associated endpoints will be evaluated in this 2-part study:

Part 1		
Primary Objectives	Endpoints	
To assess the safety, tolerability, and maximum tolerated dose (MTD) of ascending dose strengths of VP-315	
 
Discontinuations due to adverse events         (Aes); occurrence of dose-limiting toxicities         (DLTs)
 
Cutaneous Reaction Assessment (CRA)
 
	
Exploratory Objectives	Endpoints	
To evaluate the objective antitumor efficacy of VP-315	
 
Histological clearance of treated lesion(s) at excision
 
Clinical clearance of treated lesion(s) as determined by visual assessment (no tumor seen upon visible inspection) at excision
 
Estimate of remaining tumor volume (necrotic cells:tumor cells) at excision
 
Abscopal effect as determined by clinical and histological clearance of nontreated lesions at excision
 
Physician Global Assessment (PGA)
 
	
Part 2 (Coh	orts 1 and 2)	
Primary Objectives	Endpoints	
To determine the optimal regimen for dosing 8 mg of VP-315 based on safety and tolerability	
 
Treatment-related Aes; treatment-related serious adverse events (SAEs); discontinuations due to Aes; occurrence of TRAEs of special interest
 
CRA
 
	

Secondary Objectives	Endpoints		
To evaluate the antitumor efficacy of VP-315	
 
Clinical clearance of treated lesion at excision as determined by visual assessment (no residual tumor seen on visual inspection)
 
Histological clearance of treated lesion(s) at excision
 
Abscopal effect as determined by clinical and histological clearance of nontreated lesions at excision if nontreated lesions exist
 
Estimate of remaining tumor volume (necrotic cells:tumor cells) at excision
 
PGA
 
		
Exploratory Objectives	Endpoints		
• To assess the immune response to VP-315 treatment in a subset of subjects by assessing the immune repertoire in blood and in tissue	
 
Multiplex immunohistochemical staining for T-cell subsets and immune activation markers in tumor tissue samples
 
Analysis of T-cell clonality in blood and tumor tissue samples
 
		
To assess subject satisfaction with the treatment	SCAR-Q, FACE-Q		
Part 2 (Cohorts 4 and 5)			
Primary Objectives	Endpoints		
To gain additional information on the safety, tolerability, and dosing regimen of VP-315 to support a pivotal study protocol design	
 
Treatment-related Aes; treatment-related serious adverse events (SAEs); discontinuations due to Aes; occurrence of TRAEs of special interest
 
CRA
 
		
Secondary Objectives	Endpoints		
To confirm the antitumor efficacy of VP- 315 using the optimal dosing regimen determined in Part 2	
 
Clinical clearance of treated lesion at excision as determined by visual assessment (no residual tumor seen on visual inspection)
 
Histological clearance of treated lesion(s) at excision
 
Abscopal effect as determined by clinical and histological clearance of nontreated lesions at excision if nontreated lesions exist
 
Estimate of remaining tumor volume (necrotic cells:tumor cells) at excision
 
PGA
 
		

•	To characterize the pharmacokinetics (PK) of an 8 mg dose of VP-315 administered with the optimal dosing regimen determined in Part 2.	Plasma VP-315 concentrations	
Exploratory Objectives		Endpoints	
•	To assess subject and physician satisfaction with the treatment	
 
SCAR-Q, FACE-Q,
 
Scar Cosmesis Assessment and Rating (SCAR) Scale
 
	
•	To assess the immune response to VP-315 treatment in a subset of subjects by assessing the immune repertoire in blood and in tissue	
 
Multiplex immunohistochemical staining for T-cell subset and immune activation markers in tumor tissue samples
 
Analysis of T-cell clonality in blood and tumor tissue samples
 
	

**Study Design:** This is an open-label, multicenter, proof-of-concept study with a safety run-in designed to assess the safety, tolerability, MTD, and objective antitumor efficacy of VP-315 when administered intratumorally to adults with biopsy-proven BCC.

This study is expected to enroll approximately 80 subjects with a histological diagnosis of BCC in at least 1 eligible target lesion (confirmed by punch or shave biopsy).

This is a 2-part study with sequential enrollment. All enrolled subjects will receive VP-315 intratumoral injection on an outpatient basis into up to 2 target lesions:

- Part 1 (N= 2 to 8): VP- 315 once-daily dosing; starting total daily dose of 2 mg for the first subject. Ascending once-daily 1-mg dosing increments (e.g., 2 mg on Day 1, 3 mg on Day 2). Subjects may be treated for a maximum of 2 weeks and a maximum total daily dose of 8 mg in Part 1. The starting dose will be escalated between subject cohorts in 1-mg increments after the previous cohort has completed Week 1 dosing (the DLT observation period) (Figure 7-1 and Figure 7-2).
- Part 2 (N= Approximately 66 to 72): VP-315 once-daily dosing; will be a total daily dose of 8 mg in up to 5 cohorts (i.e. there were no DLTs that occurred during Part 1 and the maximum dose of 8 mg was achieved).
  - Cohort 1 (N=3-6): VP-315 once-daily dosing of 8 mg with a loading dose of half the target dose of 8 mg (i.e. 4 mg) only on W1D1; all remaining doses will be the full target dose without a loading dose. Subjects will be treated until the lesion is necrosed, for a maximum of 2 weeks (W1D1, W1D2, W1D3 and W2D1, W2D2, W2D3 up to 6 total doses).

Cohort 2 (N=3-6): VP-315 once-daily dosing of 8 mg on all treatment days (i.e., NO LOADING dose on W1D1) for up to 3 consecutive daily doses/week until the lesion is necrosed, for a maximum of 2 weeks (W1D1, W1D2, W1D3 and W2D1, W2D2, W2D3 – up to 6 total doses).

The study design and dosing strategy listed below for Cohorts 3, 4 and 5 are recommendations from the Safety Review Committee following an adhoc safety review meeting held on June 13-14, 2023 to discuss subjects reports of pain and burning at the injection site that were not observed in Part 1 of the study:

- Recommendation: Remove/skip Cohort 3 in Part 2 of the protocol and advance from Cohort 2 to Cohorts 4 and 5. Revert to Part 1 dosing strategy of a 30/70 split dose for all treatments with the injections 19dministered 15-minutes apart.
  - Cohort 3 (N=0)This cohort has been removed at the recommendation of the SRC. : This cohort has been removed upon the completion of Cohort 2.

For Part 2 (Cohorts 4 and 5) the highest total daily dose of VP-315 (8.0 mg) will be divided into a split dose; the first dose is not to exceed 2.4 mg (30% of 8-mg dose), and the remaining dose will not exceed 5.6 mg (70% of 8-mg dose) and administered 15 minutes apart (not to exceed 30 minutes).

- Cohort 4 (N=Approximately 30 [10 initial/up to 20 expansion]): (Two times weekly dosing) VP-315 once-daily dosing of 8 mg, administered on 2 consecutive days in one week (W1D1, W1D2). The planned dosing regimen will be a split dose of VP-315 for all treatments. The 500μL (8 mg) dose will be divided into 2 injections given at least 15 minutes and no more than 30 minutes apart, with 30% (150 μL) administered in the first injection and the remaining 70% (350 μL) with the second injection. Treatment for a second Target Lesion may begin on D1 of the next week (W2D1, W2D2). Each individual target lesion is treated for the assigned 2 days only (regardless of necrosis status). Up to 2 target lesions may be treated up to 4 total doses.
- Cohort 5 (N=Approximately 30 [10 initial/up to 20 expansion]): (Three times weekly dosing) VP-315 once-daily dosing of 8 mg, administered on 3 consecutive days in one week (W1D1, W1D2, W1D3). The planned dosing regimen will be a split dose of VP-315 for all treatments. The 500μL (8 mg) dose will be divided into 2 injections given at least 15 minutes and no more than 30 minutes apart, with 30% (150 μL) administered in the first injection and the remaining 70% (350 μL) with the second injection. Treatment for a second target lesion may begin on D1 of the next week (W2D1, W2D2, W2D3). Each individual target lesion is treated for the assigned 3 days only (regardless of necrosis status). Up to 2 target lesions may be treated up to 6 total doses.

See (Table 7-1)

In Part 1 of the study, each 7-day treatment week comprises up to 3 consecutive treatment days followed by a no-treatment period of at least 4 days. In Part 2 of the study, each 7-day

treatment week comprises up to 2 or 3 consecutive treatment days followed by a no-treatment period of at least 4 days. Dosing will commence in a single target lesion. In Part 1 and Part 2 Cohorts 1 and 2, once a target lesion has necrosed, treatment of that lesion stops, and treatment of a subsequent target lesion (up to 2 total, including the original target lesion) may continue on Day 1 of the following week. In Part 2 Cohorts 4 and 5, treatment of a second target lesion begins on W2D1 (not based on status of necrosis of target lesion 1).

For the first 10 subjects enrolled into Cohorts 4 and 5: after each treatment, subjects will remain in the study center for up to 2-hours post second injection for safety monitoring (e.g., continuousblood pressure, electrocardiographic and AE monitoring).

Following the final treatment of the  $10^{th}$  subject in Cohort 4, enrollment into Cohort 5 may be initiated for 10 subjects.

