# 2.3.2 Rationale for the Study Design

LTX-315 has not previously been evaluated in BCC. While the dose has been established for malignant tumors, a safe and efficacious dose has not been established in otherwise healthy subjects, for whom the alternative treatment for BCC would be surgical excision. Therefore, a safety run-in to confirm the appropriate dose range will be conducted as part of the current study.

The current study comprises 2 parts. Part 1 is designed to explore the initial VP-315 safety profile when administered in escalating doses to individual subjects with BCC, starting at 2 mg and ending at a maximum of 8 mg total daily dose to a single lesion. This strategy is intended to quickly assess the MTD and gain preliminary assessment of VP-315 induction of clinical and histological necrosis of each treated lesion while seeking to establish an AE profile for BCC. Centralized photography and Cutaneous Reaction Assessment (CRA) by the investigator will be used to document BCC response to VP-315.

During Part 1 of the study, no DLTs were reported, and escalation up to 8 mg total daily dose (the maximum dose for this study) was achieved. Therefore, Part 2 is designed to determine the optimal dosing regimen using 8 mg of VP-315 identified in Part 1 and confirm the optimal dosing regimen determined from Cohorts 4 and 5 to be used in the pivitol trial.

Pharmacokinetic data will be collected to characterize the PK of an 8 mg dose of VP-315 administered with the optimal dosing regimen in Part 2 (Cohorts 4 and 5 expansion group).

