#### **Cohort 5 expansion group:**

An SRC meeting was convened after the 10 subjects in Cohort 5 completed the Safety Assessment and approved the following:

- Up to 20 additional subjects (for a total of approximately 30 subjects) will be enrolled into Cohort 5.
- After each treatment, the additional subjects enrolled into Cohort 5 expansion: will remain in the study center for up to 1-hour (reduced from 2-hours) post second injection for safety monitoring (e.g., continuous blood pressure, electrocardiographic and AE monitoring), an additional hour may be continued at the discretion of the PI.

Plasma PK sampling will be collected in subjects in Part 2 (Cohorts 4 and 5 expansion group) as detailed in Table 8-1.

Four to 6 weeks in Part 1, and 12 to 14 weeks (Part 2) after the first injection of VP-315, subjects will return for all target and nontarget BCC lesions (Section 5.4) to be excised for histological evaluation. If the lesion(s) has clinically cleared, the area where the lesion was will be excised, and tissue samples will be sent to the central dermatopathologist for analysis/histology. Suture removal and final photography should occur 7 (±1) or 14 (±2) days after excision (7 days on the face and 14 days on the body). Subjects with excised lesions on both the face and the body will be required to complete 2 end-of-study (EOS) visits accordingly.

During the study period, subjects will be expected to visit the study facility and complete study procedures as outlined in the schedule of assessments (Table 8-1).

If there is a clinically significant AE or abnormal laboratory result at the EOS visit, follow-up (F/U) visits may be required until resolution of the abnormality, or until the condition is considered clinically stable.

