#### 7. TREATMENT AND TREATMENT PROCEDURES

## 7.1 Randomization and Blinding

This is an open-label, multicenter, dose-escalating study. Eligible subjects will be enrolled sequentially.

VP-315 will be dispensed by the study pharmacist, or designee, in an open-label fashion to the subjects. All Screening tests and procedures must be completed prior to the administration of the first dose of study drug on Day 1. Once a subject number has been assigned to a subject, it will not be reassigned to another subject. Replacement subjects may be enrolled if subjects do not complete all EOT lesion excisions. Replacement subjects will not be enrolled for subjects who discontinue the study due to treatment-related toxicity, including subjects who have not completed all lesion excisions. A new unique subject number will be assigned to the replacement subject.

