**Table 7-1 Dose Regimen (Part 2 Cohorts 1-5)** 

#### CRO must be contacted for each subject before treatment to confirm Cohort assignment

Cohorts	W1D1	W1D2	W1D3	W1D4	W2D1	W2D2	W2D3	W2D4*		
	4 mg loading	8 mg	8 mg	Safety	8 mg	8 mg	8 mg	Safety		
Cohort 1 –										
loading dose (N=3 to 6)	If 1 TRAE SI occurs in the first 3 subjects, enroll up to 6 subjects									
(* * 5 55 5)	— If no further TRAEs SI occur, then begin enrollment into Cohort 2									
	- If	2 TRAEs SI occi	ur in 6 subjects, the	en begin enrollment	into Cohort 3					
	W1D1	W1D2	W1D3	W1D4	W2D1	W2D2	W2D3	W2D4		
Cohort 2 – No	8 mg	8 mg	8 mg	Safety	8 mg	8 mg	8 mg	Safety		
loading dose (N=3 to 6)										
	• If 1 TRAE SI occurs in the first 3 subjects, begin enrollment into Cohort 4 with 30/70 split dosing of 8mg for each treatment									
Cohort 3 – has been removed										

NOTE: Cohorts 1-2: Treatment continues until TRAE (includes TRAE SI) or significant necrosis of Target Lesion #1 as determined by Sub-SRC. If significant necrosis is determined, the current assessment is changed to an assessment-only visit, and no VP-315 is administered for the remaining days of the current Treatment Interval/Week. If the subject has an additional target lesion and a TRAE has not occurred, treatment of Target Lesion #2 may begin at D1W2 of next Treatment Interval/Week. Up to 2 target lesions may be treated. Subjects that complete two weeks of treatment and the W2D4 Safety Assessment Visit without achieving complete necrosis, should return for a Limited Safety Assessment Visit on W3D1 for further evaluation of the lesion for necrosis.

Cohort 4		Lesio	n #1 Treatmei	nt	Lesion #2 Treatment						
2-day dosing regimen	W1D1	W1D2	W1D3	W2D1		W2D1	W2D2	W2D	3	W3D1	
N=30	20/70 9	20/70 9	S a fator	I ''4. J C. C.4.		20/70 9	20/70 9	Safa4		Limited	
(10 initial/ 20 expansion)	30/70 8 mg	30/70 8 mg	Safety Limited Safety		30/70 8 mg	30/70 8 mg	g Safet	y	Safety		
Cohort 5		Lesio	n #1 Treatmer	nt		Lesion #2 Treatment					
3-day dosing regimen	W1D1	W1D2	W1D3	W1D4	W2D1	W2D1	W2D2	W2D3	W2D4	W3D1	
N=30 (10 initial/	30/70 8 mg	30/70 8 mg	30/70 8 mg	Safety	Limited Safety	30/70 8 mg	30/70 8	30/70 8 mg	Safety	Limited Safety	
20 expansion)					Salety		mg			Salety	

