### **8.3. Estimate of Remaining Tumor Volume and Reduction in Tumor Volume at Excision**

Protocol endpoints reference that the estimated remaining tumor volume would be necrotic cells:tumor cells. However, estimated remaining tumor volume is the estimated volume of residual viable tumor cells. The assessment in the EDC is expressed as a percentage of viable tumor cells within the tumor bed which is composed of tumor cells (viable and necrotic), fibrosis, and inflammation.

A summary of the estimated remaining tumor volume (0 = None Remaining to 100 = All Remaining) will be provided using descriptive statistics for excised lesions (TL1, TL2, NTL1, NTL2, NTL3) from the end-of-treatment (EOT) visit. A 95% confidence interval for the mean estimated remaining tumor volume will also be provided in the summary using a one sample, two-sided t-test. Summary measures will be repeated for reduction in tumor volume (0 = No reduction to 100 = None Remaining).

The summaries will use the full analysis population, and for each lesion, descriptive statistics will be provided in the summary. The summaries will also be run using the per-protocol population as outlined in Section 6 of this SAP.

A separate listing will be provided for the excision of all lesions as described in Section 8.1 of this SAP.

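### Cohorts 4 and 5 can estimate, not confirm, efficacy of their two regimens, and the SAP gives no per-regimen clearance rate, no interval for clearance and no between-regimen difference

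*Protocol*

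**What the plan says.** **Objective.** The synopsis and Protocol Section 3 make it a secondary objective of Cohorts 4 and 5 to confirm antitumour efficacy "using the optimal dosing regimen determined in Part 2". SAP Section 2 repeats this. The primary objective of the same cohorts is to gather safety, tolerability and regimen information in support of a pivotal design.

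**Source of the regimen.** The synopsis paragraph on test product, dose and route says Cohorts 1 and 2 will determine it. Section 4.1 says Cohorts 1 and 2, or Part 1. The safety review committee's recommendation was to drop Cohort 3 and "Revert to Part 1 dosing strategy of a 30/70 split dose for all treatments". Section 2.3.2 says the aim is to "confirm the optimal dosing regimen determined from Cohorts 4 and 5 to be used in the pivitol trial".

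**Schedules and allocation.** Cohort 4 treats each target lesion for 2 days and Cohort 5 for 3 days, whether or not the lesion is necrotic. The synopsis states "This is a 2-part study with sequential enrollment", and Section 7.1 says "Eligible subjects will be enrolled sequentially". Table 7-1 adds "CRO must be contacted for each subject before treatment to confirm Cohort assignment", but the text gives no rule for choosing between the two expansion groups.

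**Analysis.** SAP 8.1, 8.2 and 8.6 give numbers and percentages by category for histologic, clinical and complete clearance. SAP 8.3 differs: "A 95% confidence interval for the mean estimated remaining tumor volume will also be provided", with the measures repeated for reduction in volume. SAP 5.5 lists Cohort 4, Cohort 4 Expansion, Cohort 5 and Cohort 5 Expansion as separate groups, with overall totals, and rules out other groupings.

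**Central reading.** Section 4.1 says "tissue samples will be sent to the central dermatopathologist for analysis/histology". Section 8.5.1 routes slide images through the central laboratory to that reader. Neither section says whether the reader knows the cohort or whether a lesion was a target lesion.

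**The concern.** To confirm a regimen, it must be fixed before the confirming data are collected, and those data must come from subjects who did not help to choose it. Here one part of the protocol treats the regimen as settled before Cohorts 4 and 5, and another settles it from them. On the second reading the same subjects both identify the regimen and confirm it.

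What is at stake is what the study report can say about each schedule when the pivotal trial is designed. Someone weighing 2 days against 3 needs the clearance rate for each schedule, its uncertainty, and the difference with its uncertainty. The planned tables supply none of these directly. They show each schedule split into an initial and an expansion group, and totals that merge the two schedules. Bare percentages from groups of 10, 26 or 27 can look like a ranking when they do not support one.

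**Working it through.** **1. The passages side by side.**

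| Place | Where the optimal regimen comes from |
|---|---|
| Synopsis and Section 3, secondary objective | Already determined, in Part 2 |
| Synopsis, test product paragraph | Cohorts 1 and 2 |
| Section 4.1 | Cohorts 1 and 2, or Part 1 |
| Section 2.3.2 | Cohorts 4 and 5 |

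The first three rows can nearly be reconciled, apart from Part 1 as a source. The fourth cannot be reconciled with them unless the word regimen has two meanings: the 30/70 split, carried over from Part 1, and the number of treatment days, which is what separates Cohort 4 from Cohort 5. The fixed 2-day and 3-day schedules at 8 mg are new. Part 1 stepped the dose up by 1 mg a day, and both Part 1 and Cohorts 1 and 2 stopped treating a lesion once it was necrotic.

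**2. Cohort sizes.** The protocol's Part 2 range reproduces: 3 + 3 + 30 + 30 = 66 and 6 + 6 + 30 + 30 = 72. SAP Section 3 gives 10 + 26 = 36 in Cohort 4 and 10 + 27 = 37 in Cohort 5, and for Part 2 as a whole 6 + 3 + 36 + 37 = 82.

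**3. What the displays contain.** SAP 8.6 defines its overall column as Cohorts 4 and 5 plus both expansions, so "Cohort 4" and "Cohort 4 Expansion" are separate groups of 10 and 26. No column holds the 36 or the 37.

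**4. Precision of a clearance rate, one lesion (TL1) per subject.** The documents give no clearance rate, so rates of 30% to 70% are assumptions. Exact (Clopper-Pearson) limits for x of n are the 2.5% quantile of Beta(x, n - x + 1) and the 97.5% quantile of Beta(x + 1, n - x).

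| Group | x/n | Exact 95% interval |
|---|---|---|
| Initial group as displayed | 5/10 | 19% to 81% |
| Cohort 4 expansion as displayed | 13/26 | 30% to 70% |
| Cohort 4 total | 11/36 | 16% to 48% |
| Cohort 4 total | 18/36 | 33% to 67% |
| Cohort 4 total | 25/36 | 52% to 84% |
| Cohort 5 total | 11/37 | 16% to 47% |
| Cohort 5 total | 19/37 | 34% to 68% |
| Cohort 5 total | 26/37 | 53% to 84% |

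**5. Precision of the difference.** Newcombe's interval combines the Wilson limits (l, u) of the two rates. For 19/37 (51.4%) these are 35.9% and 66.5%; for 18/36 (50.0%) they are 34.5% and 65.5%. The difference is 1.4 points.

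- Lower limit: 1.4 - sqrt[(51.4 - 35.9)² + (65.5 - 50.0)²] = -20.6 points.
- Upper limit: 1.4 + sqrt[(66.5 - 51.4)² + (50.0 - 34.5)²] = +23.1 points.

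As a simpler check, the half-width is 1.96 × sqrt[p(1 - p)(1/36 + 1/37)]. This is 21.0 points at p = 30% or 70%, and 22.9 points at p = 50%.

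**6. Sample used.** The 36 and 37 are SAP cohort sizes. The Full Analysis Population drops subjects without a full dose or without excision histology, so actual intervals would be somewhat wider.

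**The case against.** The study is a proof of concept with safety as the primary aim. It disclaims hypothesis testing, bases no sample size on power, and calls its efficacy evidence preliminary. On that view "confirm" is loose wording, and Section 4.1 allows Part 1 as a source, so returning to the Part 1 split is within the plan. Staging the first 10 subjects per cohort for safety review is a sound reason for sequential enrolment.

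Much of this stands, and it rules out several stronger readings that a reader might infer:

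- **That efficacy has no intervals at all.** SAP 8.3 gives one for mean tumour volume. The gap is in the clearance proportions and the between-regimen difference.
- **That histology is read unmasked.** The PGA is read at the site in an open-label study. For the central dermatopathologist the documents are silent, and specimen submission follows a laboratory manual that is not included.
- **That the better-looking arm goes forward on clearance.** No such selection rule is stated, so a best-of-two correction has no basis here.
- **That investigators could steer subjects between open expansions.** Overlap of the expansions is not stated, and assignment runs through the CRO. A case-mix bias figure would rest on invented inputs.
- **That the expansions should be randomised.** This is debatable in a safety-staged expansion. The fixed cohort sizes in the SAP suggest that the moment has passed, and randomising would not cure the imprecision.

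The disclaimer of inference does not settle what remains. It did not prevent an interval for volume, and an interval for a proportion is description in the same sense. Nor does it reconcile the objective with Section 2.3.2.

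**Conclusion.** The point holds in a limited form. The secondary objective and Section 2.3.2 disagree about where the regimen comes from. Two schedules filled without random allocation can support estimation but not confirmation. The SAP's displays give neither one clearance figure per regimen nor its uncertainty.

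At the SAP's cohort sizes and an assumed 50% clearance, a single regimen's rate is known to within about 17 points either way. Equal true rates would be compatible with observed differences of roughly 20 points in either direction: the half-width is 21 to 23 points over assumed rates of 30% to 70%. These figures assume one lesion per subject and every subject analysed, and they cover sampling error only. They say nothing about bias from non-random allocation, whose size the documents do not allow anyone to work out.

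This is a low-cost improvement to wording and reporting. It does not show a failed confirmatory test or that either schedule is wrong. Central-reader masking is a secondary point: it is unstated, not shown to be absent.

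**What to change.** 1. **Reconcile the passages.** Bring the secondary objective (synopsis, Protocol Section 3, SAP Section 2), the synopsis product paragraph, Section 4.1 and Section 2.3.2 into line on what the optimal regimen is and where it comes from. Reword the objective as estimating efficacy of the 2-day and the 3-day regimens.
2. **Add a total per regimen.** In SAP 5.5 and the efficacy displays, add Cohort 4 initial plus expansion (36) and Cohort 5 initial plus expansion (37), reduced to the Full Analysis Population. Keep the existing columns.
3. **Add intervals.** In SAP 8.1, 8.2 and 8.6, add exact 95% intervals for TL1 histologic, clinical and complete clearance in each regimen. Add a Newcombe 95% interval for the difference, labelled descriptive and non-randomised. Using TL1 keeps one lesion per subject.
4. **Code the images (secondary).** Have the central laboratory, which already relays them, send excision images under coded specimen numbers without cohort or target/nontarget status, and state this in the protocol or SAP.

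Items 1 to 3 cost a wording change and a few lines of SAS, with an entry for the SAP changes in SAP Section 14. The SAP changes need to be made before database lock, after which SAP 5.2 would class them as post hoc. Item 4 costs relabelling. If specimens have already been read, it would mean a coded re-read or a statement of what the reader knew. None of this adds subjects or alters treatment.
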